As a result of these tests and the ARGOS-01 study, modifications were made to the form of the device and the implantation procedure to improve the device's safety profile. The implant thickness was reduced from 0.9 mm to 0.5 mm overall, tapering to a rounded outer edge of only 0.1 mm, and haptics were added to the device to better maintain its positional stability and to reduce mechanical stresses of the sensor on the eye. In addition, four haptic arms and two allanoid protrusions on the posterior surface of the ring were added to the ring to improve its positional stability, facilitate unfolding and better distribute pressure on the ring. When subjected to radial force, the redesigned sensor ring did not show the abnormalities in pressure readings or the plane distortions seen in the earlier version.. The implant is also now available in three different diameters to allow selection of the implant size that best fits the individual participant. Related procedural changes, including the use of a cartridge injector similar to those used to insert foldable IOLs to insert the implant and first use of the sensor at 30 days post-surgery instead of at day 1 to 3 as in the previous study, are expected to reduce potential

 Impladata Ophthalmic Products GmbH	Clinical Investigation Plan ARGOS-02	Revision C <hr/> Page 45 of 106
---	---	------------------------------------

stress to the patients' anterior chambers during surgery and the initial post-surgical period. Together, these changes are expected to reduce irritation of the iris and pressure drifting observed in the ARGOS-01 study.

Due to the unique form of the human eye, and the exacting nature of the fit, it is not possible to assess the effects of the design modification in animals.

At this point further clinical investigations are required to assess the safety and performance of the modified ARGOS-IO system. It should become apparent in the first stage of this study if these changes were sufficient to reduce the rate of inflammatory reaction. If as anticipated the investigation is successful, an innovative device will be made available that will permit easy measurement of IOP on a daily basis in the hospital, at the ophthalmologist and/or at home. This in turn will permit more frequent and exacting adjustments to treatment, thereby slowing disease progression and the blindness that accompanies it.

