6.7 Risk/Benefit Assessment

Identified risks associated with the implantation and use of the ARGOS-IO system have been identified and minimized through the risk management process. This process, which is described in sections 6.1 to 6.5 of this CIP, and in more detail in the IB and the Risk Management Report, followed all relevant guidelines and industry standards. Unidentified residual risks of the ARGOS-IO system may remain. Although the risk profile for the patient is not expected to differ significantly from those seen with predicate devices such as IOLs and surgical procedures, that have been used in the clinical setting for decades, higher than expected safety events were seen in the ARGOS-01 study, in which an earlier ARGOS-IO implant prototype was used:

 Impladata Ophthalmic Products GmbH	Clinical Investigation Plan ARGOS-02	Revision C <hr/> Page 57 of 106
---	---	------------------------------------

- fibrin reactions (4 from 6 patients)
- pigment dispersion (6 from 6 patients)
- pupillary distortion (5 from 6 patients)

As a consequence, modifications were made to the form of the device, the implantation procedure and the eligibility criteria to mitigate risk. Ongoing collection and analysis of information about any adverse events related to the device that do occur will allow rapid identification of previously unknown risks. The implementation of a two-stage design will also prevent the exposure of further patients to the device if risks are higher than currently anticipated.

These risks are to be balanced against the medical benefit of the quasi-continuous IOP measurement permitted by the device. Ophthalmologists will obtain valuable information about individual patients to better guide their treatment, and better insight into the progression of glaucoma in general. The ability of patients to actively monitor their condition on a daily basis will motivate them to better adhere to their prescribed treatment regimen for a condition that progresses gradually with few if any short term symptoms but devastating irreversible consequences.

Given the serious and permanent long-term consequences of poor IOP control in glaucoma patients and the difficulties associated with current methods of IOP monitoring, the residual risks of the ARGOS-IO system and their probability of occurrence are clearly within the range found acceptable for other similar ophthalmic devices currently on the market.

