9.2 Sample Size Calculation

The sample size calculation was based on the study's purpose of establishing safety.

To minimize the required sample size and consequently the number of patients exposed to risk while at the same time maximizing the chances of detecting safety events, a two-stage design based on the rate of non-events was chosen (Simon, 1989). The event of interest was defined as a serious device-related adverse events (SADEs). Based on a probability of non-events of $p_0=0.75$ for the first stage and an overall acceptable probability of $p_1=0.94$, a sample size of at least 11 evaluable patients in the first stage and additional 11 patients in the second stage are required. This maintains a type 1 error probability of 5% and the power of 80% based on minimizing the maximal sample size and results in an expected sample size of 13.2 patients.

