9.3 Level of significance and the power of the clinical investigation

Significance level is set to 0.05, Power to 80%.

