The trial will be conducted as an open, prospective, multicenter single-arm clinical trial using the two- stage design described by Simon (Simon, 1989). In the first stage, 11 patients will have an ARGOS-IO pressure sensor implanted, after which enrollment will be halted until the patients have completed their 3 months follow-up visits and an interim analysis has been performed. The interim analysis will be reviewed by the DSMB. If two or more of these 11 patients in the first stage are found to have had an SADE, further enrollment into the study will be stopped. If not, enrollment will resume until another 11 patients have had an ARGOS-IO pressure sensor implanted. If two or fewer of the total 22 patients experience an SADE, a conclusion for safety will made at the 5% significance level. A corresponding 95% confidence interval for the SADE rate will be calculated according to the procedure of Koyoma (2008).

All patients who receive an ARGOS-IO implant will return for 10 follow-up visits to the clinic (day 1, 3, 10, 30, 60, 90, 120, 180, 240, 360) during the 12-month post-surgical period (see Table 6: Assessment Schedule). To allow comparison of the IOP measurement methods, IOP measurements will be made at every visit with GAT and with the ARGOS-IO systems beginning at V5 (day 30).

Ammended

The trial will be conducted as an open, prospective, multicenter single-arm clinical trial. All 22 patients will be enrolled consecutively, until a SADE occurs. In that case, the DSMB will be called, and decides whether the enrollment can be continued or not. If two or fewer of the total 22 patients experience an SADE, a conclusion for safety will made at the 5% significance level. A corresponding 95% confidence interval for the SADE rate will be calculated according to the procedure of Koyoma (2008).

All patients who receive an ARGOS-IO implant will return for 10 follow-up visits to the clinic (day 1, 3, 10, 30, 60, 90, 120, 180, 240, 360) during the 12-month post-surgical period (see Table 6: Assessment Schedule). To allow comparison of the IOP measurement methods, IOP measurements will be made at every visit with GAT and with the ARGOS-IO systems beginning at V5 (day 30).

Page 66, 8.3.3.1 Study stopping rules:

RevC

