Page 87, 9.2 Sample Size Calculation:

RevC

The sample size calculation was based on the study's purpose of establishing safety.

To minimize the required sample size and consequently the number of patients exposed to risk while at the same time maximizing the chances of detecting safety events, a two-stage design based on the rate of non-events was chosen (Simon, 1989). The event of interest was defined as a serious device-related adverse events (SADEs). Based on a probability of non-events of $p_0=0.75$ for the first stage and an overall acceptable probability of $p_1=0.94$, a sample size of at least 11 evaluable patients in the first stage and additional 11 patients in the second stage are required. This maintains a type 1 error

probability of 5% and the power of 80% based on minimizing the maximal sample size and results in an expected sample size of 13.2 patients.

Ammended

The primary aim of this study is to show “safety”, which will be evaluated based on the percentage of subjects who experience an SADE (= “non-safety), as defined in the primary endpoints.

The study will be declared a success if the final non-safety event rate is less than 6% (type II error rate of 0.20) The calculation is based on a design optimizing the minimum expected sample size with parameters $\alpha=0.05$, $\beta=0.20$, $p_0=0.75$, $p_1=0.94$. According to Table 7, those parameters will be fulfilled if 2 or less SADE will occur in a sample of 22 patients.

Part 2: Interim Analysis

Page 16, Table: Synopsis, Row: Data Analysis and Statistics, Item: Interim Analysis:

RevC

An interim analysis to assess SADE will be performed, when the first 11 patients have completed the 3 month follow-up visit.

Ammended

An interim analysis to assess Safety and Performance will be performed, when the all patients have completed the 6 month follow-up visit or if an SADE occurs.

Page 87, 9.6 Interim Analysis:

RevC

One interim analysis is planned for this study. It will take place when all patients in the first stage have completed the first 3 months of the follow-up period and will determine whether or not to continue the study to the second stage based on the number of patients experiencing an SADE..

Ammended

An interim analysis is planned for this study. It will take place when all patients have completed 6 month follow-up period, or each time an SADE occurs, prior to the regular DSMB meeting

Part 3: Implant size selection

Page 74, 8.4.4.13 ARGOS-IO implant size assessment:

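### The amended sample-size text claims a minimised expected sample size and a 0.05 error rate that hold only under the 11 + 11 rule, which the amended design sections replace

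*Protocol*

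**What the plan says.** **Rev C.** Section 9.2 requires "at least 11 evaluable patients in the first stage and additional 11 patients in the second stage", and gives an expected size of 13.2. Section 9.1 halts enrolment after 11 implants and stops the study if 2 or more of those patients have a SADE within 3 months. Safety is concluded with at most 2 SADE patients in 22. Section 9.3 reads "Significance level is set to 0.05, Power to 80" (per cent).

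**Addendum Part 1, amended text.** The amended Synopsis, 8.1.1, 8.3.3.1 and 9.1 drop the stages and the 2-of-11 limit. Amended 8.1.1 says: "All 22 patients will be enrolled consecutively, until a SADE occurs". The DSMB then decides whether enrolment goes on, and no number guides it. Amended 9.6 (Part 2) moves the interim analysis to 6 months in all patients, or to each SADE. The amended Synopsis and 9.2 nevertheless say: "The calculation is based on a design optimizing the minimum expected sample size with parameters" alpha 0.05, beta 0.20, p0 0.75 and p1 0.94. Amended 9.2 adds that 2 or fewer SADEs in 22 patients fulfil those parameters.

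**Text that the visible addendum leaves alone.** Section 6.7: "The implementation of a two-stage design will also prevent the exposure of further patients to the device if risks are higher than currently anticipated". Section 9.7 still discontinues the study if more than 1 first-stage patient has SADEs in the first 3 months.

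**SAP.** Sections 2.1, 2.10 and 8.1 combine consecutive enrolment of 22 with termination if more than 1 of the first 11 has a SADE within 3 months.

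**The concern.** Minimum expected sample size is a property of a rule that can stop early at a defined point with a calculable probability. In Rev C that was the hold at 11 with its limit of 1 SADE patient. The amended sections take both away, yet the optimality phrase and all four Simon parameters stay. The sample-size paragraph therefore no longer describes the design in the amended 8.1.1, 8.3.3.1 and 9.1.

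Two statements that reviewers of the plan rely on are affected. One is the 5% error rate for declaring the device safe. The other is the argument in 6.7 that two stages limit exposure. That argument follows directly on a report of fibrin reactions in 4 of 6 and pigment dispersion in 6 of 6 patients with the earlier prototype.

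**Working it through.** **Inputs.** SADE rate q = 0.25 (1 − p0) and q = 0.06 (1 − p1); stages of 11 + 11; limits of 1 and 2 SADE patients (Protocol 9.1, 9.2 and Table 7). No drop-out (9.4 is marked not applicable).

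Let b(n, x, q) be the binomial probability of x SADE patients in n.

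| | q = 0.25 | q = 0.06 |
|---|---|---|
| b(11, 0) | 0.0422 | 0.5063 |
| b(11, 1) | 0.1549 | 0.3555 |
| b(11, 2) | 0.2581 | 0.1135 |

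**1. Reproduce the Rev C figures.**
- P(continue at q = 0.25) = 0.0422 + 0.1549 = 0.197, so P(stop at 11) = 0.803.
- Expected size = 11 + 11 × 0.197 = 13.17, against 13.2 stated.
- P(success) = b(11,0) × P(X2 ≤ 2) + b(11,1) × P(X2 ≤ 1).
- At q = 0.25: 0.0422 × 0.4552 + 0.1549 × 0.1971 = 0.0497 (alpha).
- At q = 0.06: 0.5063 × 0.9752 + 0.3555 × 0.8618 = 0.8001 (power).

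A full search over two-stage designs with N up to 40 finds this design to be both the optimal and the minimax one. The claim was correct for Rev C.

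**2. Amended rule read as one stage** (22 patients, at most 2 SADE patients, no binding stop).
- Planned size: 22 at any SADE rate.
- Type I error: 0.0018 + 0.0131 + 0.0458 = 0.0606.
- Power: 0.2563 + 0.3600 + 0.2413 = 0.8576.

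The difference from step 1 is the path that the stage-1 limit closed: 2 SADE patients in the first 11 and none in the next 11. It adds 0.2581 × 0.0422 = 0.0109 to alpha (0.0497 + 0.0109 = 0.0606) and 0.1135 × 0.5063 = 0.0574 to power. The smallest one-stage design that meets 0.05 and 0.80 has 23 patients with at most 2 SADE patients (alpha 0.0492, power 0.843).

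**3. Amended rule with DSMB discretion.** The expected size depends on a choice that the plan does not state. At q = 0.25, and assuming that each SADE is known at once:
- enrolment ended at the first SADE: (1 − 0.75^22) / 0.25 = 3.99;
- enrolment ended at the third SADE: 11.69;
- enrolment never ended: 22.

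No single expected size exists, so none is minimised.

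**4. Does the surviving limit in 9.7 and the SAP secure 13.2?** Only if implantation is held at 11 until the eleventh patient has 3 months of follow-up. Assume 22 implants spread evenly over the planned 6 months, without pauses. The eleventh is then implanted at about month 3 and reaches 3 months of follow-up at about month 6, when all 22 are implanted. Without a hold, the limit can end the study but cannot keep the number implanted near 13.

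**The case against.** **A numerical stop survives.** A reader might infer that the amended plan has none. The documents do not support that: 9.7 keeps one, and so do SAP 2.1, 2.10 and 8.1. This stands. The amended sections and 9.7 therefore disagree, and the first stage that 9.7 names is no longer defined in the amended design.

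**A halt is still mentioned.** Protocol 11.1.7 and SAP 5.4 say that enrolment is halted for a DSMB review once the 11 first-stage patients have completed 3 months. Neither says that implantation stops at the eleventh patient. SAP 2.10 also plans an interim analysis with 11 to 14 patients enrolled and only 1 month of follow-up. SAP 8.2 records that the first two DSMB meetings took place after 6 patients had completed Visit 4 and after 11 had completed Visit 5. A hold at 11 is not clear from this.

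**Protection was replaced, not simply deleted.** A reader might infer that exposure control is gone. Amended 8.3.3.1 stops enrolment at a SADE. Assume even accrual over 6 months, SADE onset uniform over 90 days and a 25% rate. On average about 8 patients are then implanted when the first SADE is known, and the pause comes at or before 11 implants in about 81% of simulated runs, close to the 80.3% for the Rev C stop. This also stands, with the limit that a pause is not a binding stop.

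**Section 5.3.** It says "It should become apparent in the first stage of this study if these changes were sufficient to reduce the rate of inflammatory reaction". A reader might take this as justifying the risk by the first stage. It is an expectation about what will be learned, and the point does not rest on it. Nor do the documents show what patients were told, because no consent text is available.

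**Conclusion.** The optimality phrase and the 0.05 error rate in the amended Synopsis and 9.2 are wrong for the design in the amended 8.1.1, 8.3.3.1, 9.1 and 9.6. Without a binding stage-1 stop, the type I error at a 25% SADE rate is 0.0606 rather than 0.0497, power is 0.858 rather than 0.800, and the planned size is 22 rather than an expected 13.2. The error-rate excess is small. The larger defect is that the amended sections, 6.7, 9.7 and the SAP describe different designs, and none of them clearly secures the expected size that the phrase implies.

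The one-stage figures assume 22 evaluable patients and no DSMB stop. The visible addendum amends Rev C and its text ends at Part 3. The SAP follows Rev. G, which is not available. A later correction to 6.7, 9.2 or 9.7 is therefore possible.

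**What to change.** Reconcile the amended Synopsis, 8.1.1, 8.3.3.1, 9.1 and 9.2 with 9.7 and the SAP (2.1, 2.10, 8.1), and check 11.1.7 and SAP 5.4 at the same time. The sponsor must state which of two cases applies.

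- **No stage-1 hold.** Delete the optimality phrase from the Synopsis and 9.2. State that up to 22 patients are implanted unless the DSMB ends enrolment, with type I error 0.061 and power 0.86 for at most 2 SADE patients in 22. Stating a fixed 22 beside an unchanged alpha of 0.05 would not be correct. In 6.7, describe the pause and DSMB review in place of the two-stage protection, and bring 9.7 and the SAP into line.
- **Stage-1 rule with a hold at 11.** Say so in the amended sections and the SAP. The optimality claim, the 13.2 and the text of 6.7 can then stay.

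The cost is redrafting. In the first case, the stated error rate and the exposure statement become slightly less favourable.

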9.5 Pass/fail criteria to be applied to the results of the clinical investigation

This investigation will be considered a success if fewer than two of the total 22 patients (stage 1 and 2) experience SADEs during the follow-up period.

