9.7 Criteria for termination of the clinical investigation on statistical grounds

The participation of an individual site in the study will be discontinued if the sponsor, the investigator or the responsible ethics committee deems it necessary for any reason.

The complete study will be discontinued:

 Impladata Ophthalmic Products GmbH	Clinical Investigation Plan ARGOS-02	Revision C
		Page 85 of 106

- If the sponsor and/or any responsible regulatory authority or ethic committee judge/s it necessary for any reason. See also section 8.9 Early Patient Withdrawal and section 12.10 Criteria for Suspension and Premature Termination of Study
- If, during the course of the study, the DSMB comes to the conclusion that further implantation of the ARGOS-IO pressure sensor would subject study patients to undue risk
- If more than 1 patient in the first stage of the study experiences SADEs during the first 3 months of the post-surgical follow-up period.

Patients who until that time had had an ARGOS-IO pressure sensor implanted will continue to be followed up.

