- Zou, G. (2011). Confidence interval estimation for the Bland-Altman limits of agreement with multiple observations per individual. *Stat Methods Med Res, S.* 0 (0): 1-13.

Addendum to Clinical Investigation Plan: A prospective, open-label, multicenter clinical investigation to assess the safety and performance of ARGOS-IO system in patients with Primary Open Angle Glaucoma (POAG)

To Current Revision: ARGOS-02_CIP_RevC_20140218

Part 1: Enrollment

Page 8, Table: Synopsis, Row: Study Design:

RevC

This clinical investigation prospective, open-label, multicenter, single-arm clinical investigation will be conducted in two stages using a Simon two-stage design. Subjects will be enrolled as follows:

First stage: 11 patients

Second stage: 11 patients

An interim analysis will be performed when the 11 patients of the first stage have completed their 3 month follow-up visits. The trial will be stopped if 2 or more patients have experienced a serious adverse device events (SADE) at this time. Otherwise enrollment will be resumed and the trial continued until an additional 11 patients have been enrolled in stage 2 and received ARGOS-IO implants. A conclusion for safety will be made if in total no more than 2 of the total of 22 patients experience an SADE.

Ammended

This prospective, open-label, multicenter, single-arm clinical investigation will enroll 22 consecutive Patients.

Enrollment will be temporarily halted in case a serious adverse device effect (SADE) occurs, and a Data and safety Monitoring Board (DSMB; see section "Safety Monitoring" on page 16) meeting will be conducted as soon as possible. The DSMB will then recommend whether to further continue the study as planned, or whether enrollment shall be stopped. A conclusion for safety will be made if in total no more than 2 of the total of 22 patients experience an SADE.

Page 8, Table: Synopsis, Row: Sample Size Considerations:

RevC

The primary aim of this study is to show "safety", which will be evaluated based on the percentage of subjects who experience an SADE (= "non-safety"), as defined in the primary endpoints.

For the study as a whole, "safety" will be determined based on the following decision rule: if in stage 1 the non-safety event rate is greater than 25%, the trial will be stopped (type 1 error rate of 0.05). If

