the non-safety event rate is lower than 25%, the study will be continued into stage 2. It will be declared a success if the final non-safety event rate is less than 6% (type II error rate of 0.20) The calculation is based on a two-stage Simon design optimizing the minimum expected sample size with parameters $\alpha=0.05$, $\beta=0.20$, $p_0 = 0.75$, $p_1 = 0.94$.

Ammended

The primary aim of this study is to show "safety", which will be evaluated based on the percentage of subjects who experience an SADE (= "non-safety"), as defined in the primary endpoints.

The study will be declared a success if the final non-safety event rate is less than 6% (type II error rate of 0.20) The calculation is based on a design optimizing the minimum expected sample size with parameters $\alpha=0.05$, $\beta=0.20$, $p_0 = 0.75$, $p_1 = 0.94$.

Page 16, Table: Synopsis, Row: Safety Monitoring:

RevC

A data safety monitoring board (DSMB) will be established prior to enrollment of the first patient. The DSMB is to review the safety data, including SAEs/SADEs, on a regular basis and will advise on any changes required in the conduct this clinical investigation. The DSMB will also review the data of the interim analysis and give recommendations to the Sponsor to either continue the clinical investigation (with or without an amendment of the clinical investigation plan) or to stop enrolment into the clinical investigation based on safety concerns.

Ammended

A data safety monitoring board (DSMB) will be established prior to enrollment of the first patient. The DSMB is to review the safety data, including SAEs/SADEs, on a regular basis, or if a SADE occurs, and will advise on any changes required in the conduct of this clinical investigation.

Page 60, 8.1.1 Description of the type of clinical investigation:

RevC

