As described in section 9, the study will be conducted in two stages. In the first stage, 11 subjects will receive ARGOS-IO implants, after which implantation will be halted. Once these subjects have completed their 3 months follow-up visits, the interim results will be evaluated by the DSMB. The study will be stopped for safety reasons if at the time of the interim analysis two or more of these 11 subjects have had SADEs or if the DSMB otherwise determines that severe safety risks to the subjects exist.

If more than two patients in the first stage of the study experience SADEs, the study will be stopped for safety reasons.

The study may be discontinued at any time for administrative reasons; if new negative data about the investigational device resulting from this or any other studies becomes available; and/or on advice of the DSMB, the sponsor, the investigators, and/or the EC or regulatory authorities.

If the study is prematurely terminated or suspended, the sponsor will promptly inform the investigators, the Regulatory Authorities and the ECs of the reason for termination or suspension. If the study is prematurely terminated for any reason, the investigator should promptly inform the study subjects and assure they receive appropriate therapy and/or follow-up.

The study can be terminated at any time for any reason by the sponsor.

Ammended

Enrollment will be stopped at the occurrence of a SADE. At this point, a DSMB meeting will be called. The DSMB will then evaluate the SADE, and decides as to whether enrollment will be ended, and will also decide on how to proceed further with the conduct of the study.

The study may be discontinued at any time for administrative reasons; if new negative data about the investigational device resulting from this or any other studies becomes available; and/or on advice of the DSMB, the sponsor, the investigators, and/or the EC or regulatory authorities.

If the study is prematurely terminated or suspended, or enrollment is stopped, the sponsor will promptly inform the investigators, the Regulatory Authorities and the ECs of the reason for termination or suspension or stop of enrollment. If the study is prematurely terminated for any reason, the investigator should promptly inform the study subjects and assure they receive appropriate therapy and/or follow-up.

The study can be terminated at any time for any reason by the sponsor.

Page 84, 9.1 Statistical design, method and analytical procedures:

RevC

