The primary purpose of this investigation is to assess safety of the investigational device. This will be judged statistically based on the number of individual patients experiencing serious device-related adverse events (SADEs). The study will be implemented in a two-stage design equivalent to the Simon optimum design to minimize the expected sample size (Simon, 1989). In the first stage, enrollment will be halted after 11 patients have received ARGOS-IO implants. An interim analysis will be conducted when these 11 patients have been followed-up for 3 months. If two or more patients experience SADEs in this time, the study will be stopped for safety reasons (Type I error rate = 0.05). If fewer than two have experienced SADEs, enrollment will be resumed and will be continued until a total of 22 patients have received ARGOS-IO implants. A final decision for safety will be drawn, if overall two or fewer of the total 22 patients have an SADE [SIMON optimum two stage design to minimize expected sample sizes, parameters: $\alpha=0.05$, $\beta=0.20$, $p_0 = 0.75$ (proportion in stage 1 without SADE), $p_1 = 0.94$ (proportion overall without SADE)]. A corresponding 95% confidence interval for the proportion of the safety population with SADEs will be calculated using the method proposed by Koyoma and Chen (2008).

Table 1. Study design

	First Stage	Overall
SADE-free Subjects		
Proportion	$p_0 = 0.75$	$p_1 = 0.94$
Minimum number required	10	20
Subjects with SADE		
Proportion	$1 - p_0 = 0.25$	$1 - p_1 = 0.06$
Maximum number allowed	1	2
Total Number of Subjects	11	22

Ammended

The primary purpose of this investigation is to assess safety of the investigational device. This will be judged statistically based on the number of individual patients experiencing serious device-related adverse events (SADEs). Patients will be enrolled consecutively until a total of 22 patients have received ARGOS-IO implants. A final decision for safety will be drawn, if overall two or fewer of the total 22 patients have an SADE [parameters: $p_1 = 0.94$ (proportion overall without SADE)]. A corresponding 95% confidence interval for the proportion of the safety population with SADEs will be calculated using the method proposed by Koyoma and Chen (2008).

Table 2. Study design

		Overall
SADE-free Subjects		
Proportion		$p_1 = 0.94$
Minimum number required		20
Subjects with SADE		
Proportion		$1 - p_1 = 0.06$
Maximum number allowed		2
Total Number of Subjects		22

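### Amended CIP 8.1.1 and 9.2 attach the 5% level to 2 or fewer SADE patients of 22, a rule whose type I error reaches 6.06%; CIP 9.5, CIP 9.7 and the SAP give other rules

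*Protocol*

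**What the plan says.** CIP Rev. C (9.1, Table 7, 9.2) describes a Simon two-stage design: 11 patients, stop if 2 or more have a SADE; otherwise 11 more, and conclude safety if no more than 2 of 22 have one. It states type I error 5%, power 80% and an expected sample size of 13.2.

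Addendum Part 1 removes the stages:

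- **Amended 9.1:** "Patients will be enrolled consecutively until a total of 22 patients have received ARGOS-IO implants". The amended design table has no First Stage column.
- **Amended 8.3.3.1:** enrolment pauses at any SADE. "The DSMB will then evaluate the SADE, and decides as to whether enrollment will be ended". No fixed limit remains.
- **Amended Synopsis (Study Design):** "A conclusion for safety will be made if in total no more than 2 of the total of 22 patients experience an SADE".
- **Amended 8.1.1:** for two or fewer of 22, "a conclusion for safety will made at the 5% significance level".
- **Amended 9.2:** after restating alpha 0.05, beta 0.20, p0 0.75 and p1 0.94, it says "those parameters will be fulfilled if 2 or less SADE will occur in a sample of 22 patients".

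Two other rules remain in the text:

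- **First-11 limit.** CIP 9.7, which the visible addendum does not touch, ends the study: "If more than 1 patient in the first stage of the study experiences SADEs during the first 3 months of the post-surgical follow-up period". SAP 2.1, 2.10, 8.1 and Table 2 also keep the limit, and SAP 7.2 refers to Simon's optimal two-stage rule. SAP 2.5, however, concludes on at most 2 of 22 without mentioning the limit.
- **At most 1 of 22.** The amended Synopsis (Sample Size row) and amended 9.2 say "The study will be declared a success if the final non-safety event rate is less than 6" percent. CIP 9.5 says the study is "considered a success if fewer than two of the total 22 patients (stage 1 and 2) experience SADEs during the follow-up period".

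**The concern.** The 5% level and 80% power were calculated for a rule with two limits. The addendum keeps those operating characteristics but deletes one of the limits. Success then includes an extra path, 2 SADE patients in the first 11 and none in the next 11, and that path adds to the type I error.

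SAP 5.3 states that the primary safety variable is the only one tested, so this rule carries all of the trial's formal inference. If the documents give three different rules, the choice among them could be made after the SADE count is known, in an open-label trial that has already had interim reports (SAP 8.2).

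**Working it through.** **Inputs.** SADE rate q = 0.25 under the null (1 − p0) and 0.06 under the alternative (1 − p1), from CIP 9.2 and SAP 2.9. Alpha 0.05 and power 80% from CIP 9.3. Let X1 and X2 be the numbers of SADE patients in the first and second 11, independent and binomial. SADEs are counted within 3 months under every rule, all 22 patients are evaluable, and there is no extra DSMB stop.

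**Step 1. Reproduce the plan's figures (at most 1 of 11, at most 2 of 22).**

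P(success) = P(X1=0)·P(X2≤2) + P(X1=1)·P(X2≤1)

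- q = 0.25: 0.0422 × 0.4552 + 0.1549 × 0.1971 = 0.0192 + 0.0305 = **0.0497**
- q = 0.06: 0.5063 × 0.9752 + 0.3555 × 0.8618 = 0.4938 + 0.3064 = **0.8001** (from unrounded terms)
- Expected sample size at q = 0.25: 11 + 11 × (0.0422 + 0.1549) = 11 + 11 × 0.1971 = **13.2**

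All three agree with Rev. C 9.2, so the stated 5% and 80% belong to the rule with the first-11 limit.

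**Step 2. The amended rule alone (2 or fewer of 22).**

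- P(Bin(22, 0.25) ≤ 2) = **0.0606**
- P(Bin(22, 0.06) ≤ 2) = **0.8576**

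The difference in type I error is 0.0606 − 0.0497 = 0.0109. This equals the added path: P(X1=2)·P(X2=0) = 0.2581 × 0.0422 = 0.0109.

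**Step 3. The stricter rule.** 1/22 = 4.5% is below 6% and 2/22 = 9.1% is not, so a final rate under 6% and fewer than two of 22 both mean at most 1 of 22.

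- P(Bin(22, 0.25) ≤ 1) = **0.0149**
- P(Bin(22, 0.06) ≤ 1) = **0.6163**

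**Step 4. Compare the rules.**

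| Rule | Where | Type I error (q = 25%) | Power (q = 6%) |
|---|---|---|---|
| At most 2 of 22 | Amended 8.1.1, 9.1, 9.2; SAP 2.5 | 6.06% (ceiling) | 85.8% |
| At most 1 of first 11 and at most 2 of 22 | CIP 9.7 with the final limit; SAP 2.1, 7.2, Table 2 | 4.97% | 80.0% |
| At most 1 of 22 | CIP 9.5; 6% wording in amended Synopsis and 9.2 | 1.49% | 61.6% |

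**Step 5. How often the rules disagree.**

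| Outcome | q = 6% | q = 10% | q = 25% |
|---|---|---|---|
| 2 in first 11, 0 in next 11: success under amended 8.1.1, termination under CIP 9.7 | 5.7% | 6.7% | 1.1% |
| Exactly 2 of 22: success under amended 8.1.1, failure under CIP 9.5 | 24.1% | 28.1% | 4.6% |

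The 10% column is an illustrative rate between the two design values.

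**The case against.** The best reply is that the level is already protected. The SAP keeps the first-11 limit in several places, expressly to respect Simon's design, and CIP 9.7 keeps it too. A first-stage limit and a final limit are two parts of one design, so amended 8.1.1 and CIP 9.7 can be read together. Amended 9.2 also points to Table 7, which in Rev. C contains the first-stage limit. If that reading governs, type I error is 4.97%. This stands as a statement about the SAP. It does not rescue the amended CIP text, because amended 8.3.3.1 puts DSMB judgement in place of the limit and the amended design table has no First Stage column. It also leaves SAP 2.5 at odds with SAP 2.1.

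Second, the excess is small: about 1 percentage point, at the null boundary, and only if the DSMB always lets enrolment continue. That is right; 6.06% is a ceiling, and any DSMB stop lowers it.

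Third, the at-most-1 rule may be loose wording: the 6% figure may simply restate p1, and CIP 9.5 may be a slip for two or fewer. CIP 9.5 also counts events over the follow-up period, so 1.49% and 61.6% rest on assuming a 3-month window. This is plausible, but 9.5 is the section headed as the pass/fail criteria, and as written it contradicts the others.

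Fourth, the SAP is written to CIP Rev. G, which was not supplied, and the addendum text available stops at Part 3. A later correction cannot be excluded.

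**Conclusion.** The concern holds for CIP Rev. C with its visible addendum and for the SAP. Amended 8.1.1 and 9.2 claim 5% for a rule whose type I error is up to 6.06%. Of the three rules in the documents, only the one with the first-11 limit meets both the 5% level and 80% power. The numerical excess is modest. The larger problem is that 2 SADE patients of 22, a result with probability 24.1% at the design's own 6% rate, has no single pre-specified meaning.

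The figures assume 22 evaluable independent patients, a 3-month window under every rule, and no additional DSMB stop. This should be corrected. Confidence is medium, because Rev. G might already have changed the CIP text.

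**What to change.** 1. In amended 8.1.1, 8.3.3.1 and 9.1, restore the limit: the study is terminated and safety is not concluded if more than 1 of the first 11 implanted patients has a SADE within 3 months of implantation. Put the First Stage column (11 patients, maximum 1) back in the amended 9.1 table.
2. State one success rule, at most 1 of the first 11 and at most 2 of the 22 patients with a SADE within 3 months, in the amended Synopsis (Study Design and Sample Size rows), 8.1.1, 9.1, 9.2, CIP 9.5, and SAP 2.1 and 2.5. It replaces the 6% criterion in the amended Synopsis and 9.2 and the criterion in 9.5.
3. State in SAP 7.2 that the first-11 limit is a fail criterion at the final analysis even if enrolment did not pause at 11. This part can still take effect: SAP 8.2 records a DSMB look at 11 patients at one month, no look at the first 11 at 3 months, and all subjects past Visit 9. Type I error and power are 4.97% and 80.0% whether the limit is applied as a pause or at the end.

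**Cost.** No added patients, visits or procedures. Power at a 6% SADE rate is the planned 80.0%, not 85.8%. The CIP edits change decision rules, so CIP 12.3 requires a formal amendment and ethics committee approval. The rule is more lenient than CIP 9.5, so it should be recorded as harmonisation with Rev. C Table 7, CIP 9.7 and SAP Table 2, and dated before hard lock of the database. Check Rev. G first, since some of this may already be done.
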